# 3.2. Study Outcome Measures

# 3.2.1. Safety Outcomes

All safety outcomes will be assessed in the safety analysis population of all subjects who received one or more doses of study product. Outcomes will be reported by treatment arm.

- Primary Safety Outcome
  - Number of subjects reporting solicited urogenital AEs following the first dose of the study product through Visit 2 (Day 8-15).
  - Number of subjects reporting serious adverse events (SAEs) considered product-related following the first dose of the study product through Visit 3 (Day 22-31)
- Secondary Safety Outcomes
  - Number of subjects experiencing non-laboratory non-solicited AEs following the first dose of the study product through Visit 3 (Day 22-31).

• Number of subjects experiencing laboratory AEs following the first dose of the study product through Visit 2 (Day 8-15).

# 3.2.2. Efficacy Outcomes

# 3.2.2.1. Primary and Secondary Efficacy Outcomes

- Primary Efficacy Outcome Proportion of subjects with clinical cure in each study arm at Visit 2 (Day 8-15).
- Secondary Efficacy Outcomes
  - Proportion of subjects with therapeutic cure in each study arm at Visit 2 (Day 8-15) and at Visit 3 (Day 22-31).
  - Proportion of subjects with Nugent score of 3 or less (negative for BV) and 4-6 (intermediate) in each study arm at Visit 2 (Day 8-15) and at Visit 3 (Day 22-31).
  - Proportion of subjects with clinical cure in each study arm at Visit 3 (Day 22-31).

# 3.2.2.2. Exploratory Efficacy Outcomes

- Proportion of subjects with clinical cure in each study arm by subgroup (first time or recurrent infection) by Visit 2 (Day 8-15) and by Visit 3 (Day 22-31).
- Proportion of subjects with therapeutic cure in each study arm by subgroup (first time or recurrent infection) by Visit 2 (Day 8-15) and by Visit 3 (Day 22-31).
- Mean count of *Lactobacillus spp.*, *Gardnerella spp.*, and *Mobiluncus spp.*, respectively, in each study arm at baseline, Visit 2 (Day 8-15) and at Visit 3 (Day 22-31).
- Mean fungal colony count in vaginal secretions in each study arm at baseline, at Visit 2 (Day 8-15) and at Visit 3 (Day 22-31).

## 4. STUDY DESIGN

This is a Phase 2, double-blind, randomized, placebo-controlled, multi-center trial enrolling 120 subjects with BV who will be randomized at a ratio of 2:1 to receive active test article (5% Monolaurin Vaginal Gel) or placebo (Vehicle Placebo Gel). There will be three clinic visits over 31 days.

The study will seek women 18-50 years old with signs and symptoms of BV. Subjects may be identified during a routine clinic visit, referred by their care provider, or may be recruited directly to the research clinic. For women recruited following a clinic visit, the study team may review the Amsel criteria with the nonstudy clinician, but the expectation is that these tests will be repeated by study personnel to document each component of the Amsel testing after the subject has signed an informed consent.

Subjects will be educated about the study and will be asked to sign an informed consent prior to any evaluation.

Eligibility will be reviewed and if subjects qualify for participation, demographics, a medical history, including number of episodes of BV in the past year, concomitant medications review, and a physical exam including a gynecological exam will be performed. Women of childbearing potential will undergo a urine pregnancy test. Vaginal swabs will be taken to perform a KOH test, vaginal pH, and to review a wet prep. Subjects must have evidence of BV using the Amsel criteria (subjects must have any three of the four Amsel criteria: presence of discharge, greater than or equal to 20% clue cells on wet prep, positive "whiff test" on KOH prep, vaginal pH of greater than 4.5). Vaginal swabs for Gram stain of vaginal smear, and assessment for Candida spp., selected bacterial species, Trichomonas vaginalis, Chlamydia trachomatis, and Neisseria gonorrhoeae will be collected. Those with clinical evidence of active genital ulcer disease or evidence of trichomonas on wet prep or OSOM® test will be excluded from the study. Blood samples will be collected for safety assessments (HIV, WBC count, hemoglobin, platelets, neutrophil count, creatinine, aspartate aminotransferase [AST], alanine aminotransferase [ALT], total bilirubin, random glucose). Subjects who continue to qualify for participation will be randomized at a ratio of 2:1 to receive 5% Monolaurin Vaginal Gel or Vehicle Placebo Gel administered vaginally morning and night for 6 consecutive doses (3 days). All subjects will be provided a 5-day memory aid to assess for local solicited events with instruction on use prior to discharge. The investigational drug (active test article or placebo) will be supplied in a kit containing sufficient prefilled vaginal applicators for six consecutive doses over 3 days. Subjects will be instructed on the proper use of the applicators and the first dose will be self-administered with observation by study personnel in the clinic. Subjects will be instructed to refrain from sexual intercourse including receptive oral sex or insertion of substances or objects intravaginally between Visit 1 and Visit 2 and 48 hours prior to Visit 3. Subjects who experience a new or worsening solicited reactogenicity symptom that is grade 2 or higher will be asked to contact the study site to confirm the severity. A determination will be made whether to continue or discontinue the study product by a licensed study clinician. No investigational or commercial agents or therapies other than test article may be administered with the intent to treat the subject for BV. For all treatment groups, each subject will be evaluated in the clinic at screening and at Visit 2 (Day 8 [Window Days 8-15]) and Visit 3 (Day 28 [Window Days 22-31]) following study drug administration.

Visit 2 (Day 8 [Window Days 8-15]): At this visit, the study team will review the memory aid, the intercurrent medical history with assessment of AEs and SAEs, changes to the concomitant medications, a gynecological exam and a targeted physical exam based on symptoms will be performed, and vaginal pH and vaginal swabs for Gram stain, saline wet mount, KOH 10% wet mount and culture will be obtained. If signs and symptoms of vaginitis fail to resolve, the study clinician will refer the subjects to their clinician for standard treatment for BV or other etiologies of vaginitis at the clinician's discretion and the subject will be classified as a clinical failure at Visit 2 and/or 3. Follow-up hematology and chemistry labs (WBC count, hemoglobin, platelets, neutrophil count, creatinine, AST, ALT, total bilirubin, random glucose) for safety evaluation will be performed.

Visit 3 (Day 28 [Window Days 22-31]) will include a review of the intercurrent medical history, concomitant medications, AEs and SAEs, and a gynecological exam and a targeted physical exam based on symptoms. Vaginal pH and vaginal swabs for Gram stain, saline wet mount, KOH 10% wet mount and culture will be performed.

Subjects who have positive HIV, *Chlamydia*, or *Neisseria gonorrhoeae*, or a grade 3 laboratory results from Visit 1 will be contacted within 24 hours of receipt of laboratory results and will be asked to follow up with their provider. These subjects will be asked to discontinue the study therapy if the test result returns during the study product administration period of the study.

These subjects will continue in efficacy and safety follow up.

At visits 1, 2 and 3, an extra vaginal swab will be collected for future use, if subject consents to future use of specimens.

# 4.1. Substudies (if applicable)

None

## 5. STUDY ENROLLMENT AND WITHDRAWAL

# 5.1. Subject Inclusion Criteria

It is the intent of this study to enroll women who are generally healthy with evidence of BV on gynecological evaluation. Subjects may have asymptomatic BV, but must meet any three of the four Amsel criteria for BV as defined in section 7.1. Inclusion criteria must be assessed by a clinician licensed to make medical diagnoses. Subjects must meet all of the following inclusion criteria to participate in this study:

- 1. Non-pregnant, non-breastfeeding females between the ages of 18 and 50 years, inclusive.
- 2. Women of childbearing potential\* must agree to practice reliable contraception\*\* for the 28-day period before enrollment through 30 days following treatment.
  - \*(not surgically sterile via tubal ligation, bilateral oophorectomy or hysterectomy, or who have not been postmenopausal for  $\geq 1$  year)
  - \*\* Acceptable birth control methods for the purposes of this study may include, but are not limited to, abstinence from intercourse with a male partner, monogamous relationship with vasectomized partner, barrier methods to include condoms and diaphragms, intrauterine devices, and licensed hormonal methods. NuvaRing® contraceptive use will be prohibited from this study since the device can alter vaginal secretions.
- 3. Presenting with signs of BV (as per Amsel Criteria). Subjects must meet any three of the four criteria for enrollment\*
  - \*Presence of discharge, greater than or equal to 20% clue cells on wet prep, positive "whiff test" on KOH prep, vaginal pH of greater than 4.5.
- 4. Not currently menstruating or expected to in the next 4 days.
- 5. Able to understand and comply with planned study procedures.
- 6. Willing to abstain from sexual intercourse, insertion of tampons, douches, or other intravaginal medications or objects between Visit 1 and Visit 2 and 48 hours prior to Visit 3.
- 7. Provide written informed consent before initiation of any study procedures and be available for all study visits.
- 8. No known history of HIV.

# 5.2. Subject Exclusion Criteria

Subjects who meet any of the exclusion criteria at Visit 1 will be excluded from study participation. Exclusion criteria must be assessed by a clinician licensed to make medical diagnoses. Subjects will not be able to participate if they have any of the following:

- 1. Signs or symptoms of vaginal/cervical/pelvic infection on screening or clinical diagnosis of vaginal/cervical/pelvic infection in the past 14 days.
  - \*(including but not limited to yeast vulvovaginitis, chlamydia, gonorrhea, trichomonas, genital ulcer disease, pelvic inflammatory disease). Self-treatment for presumed yeast vaginitis is not an exclusion if treatment was discontinued 7 days or greater prior to enrollment.
- 2. Treatment for BV within the past 14 days.
- 3. Cervical or vaginal high grade squamous intraepithelial dysplasia (HSIL), atypical glandular cells of uncertain significance (AGUS) or cervical intraepithelial neoplasia grade 2 (CIN2) or higher\*
  - \*Atypical squamous cells of undetermined significance (ASCUS), low grade squamous intraepithelial lesion (LSIL) or cervical intraepithelial neoplasia grade 1 (CIN1) are acceptable. Individuals with a history of atypical glandular cells of uncertain significance (AGUS), HSIL or CIN2 and who have received subsequent evaluation and/or treatment with follow up normal PAP smear are eligible. Patient report will be accepted.
- 4. History of undiagnosed vaginal bleeding.
- 5. Use of a systemic, vaginal, or perineal antibiotic within 7 days prior to enrollment in this study.
- 6. Use of an immunosuppressive or immunomodulatory drug\* for two or more consecutive weeks within 6 months prior to enrollment
  - \*such as >0.5 mg/kg/day or  $\ge 20$  mg total dose/day of prednisone orally or > 800 µg of inhaled beclomethasone (nasal and non-genital topical steroids are allowed).
- 7. History of allergic reactions attributed to compounds of similar chemical or biologic composition to Monolaurin Vaginal Gel.
- 8. Uncontrolled concurrent illness\*. Subjects with a history of organ or marrow transplant are excluded.
  - \*Including, but not limited to, ongoing or active infection, active liver, kidney or autoimmune diseases (a history of thyroid disease will be permitted as long as the thyroid disease is now stable), symptomatic congestive heart failure, unstable angina pectoris, cardiac arrhythmia, or psychiatric illness/social situations that would limit compliance with study requirements.
- 9. Acute illness within 3 days before receipt of study product (per investigator's discretion).
- 10. Pregnant women and women who are planning to become pregnant within 30 days after the final study dose, or women who are breastfeeding.
- 11. Immunosuppression as a result of an underlying illness or treatment or use of anticancer chemotherapy or radiation therapy (cytotoxic) within the preceding 36 months.
- 12. Active neoplastic disease\* or a history of any hematologic malignancy. Active neoplastic disease is defined as neoplastic disease or treatment for neoplastic disease within the past 5 years.

- \*(excluding non-melanoma skin cancer)
- 13. Received an experimental agent\* within 30 days before receipt of study product or expect to receive an experimental agent during the 1 month study period.
  - \*(vaccine, drug, biologic, device, blood product, or medication)
- 14. Any condition that would place the subject at an unacceptable risk of injury, render her unable to meet the requirements of the protocol, or that may interfere with successful completion of the study.
- 15. A history of alcohol or drug abuse\* during the previous 1 year that in the opinion of the site investigator would interfere with study procedures
  - \*For example, daily excessive alcohol use or frequent binge drinking as determined by the investigator, or daily marijuana use.

# **5.3.** Treatment Assignment Procedures

Subjects, study site and laboratory personnel will be masked to the treatment assignments of study subjects.

#### 5.3.1. Randomization Procedures

Subjects will be randomly assigned to active drug or placebo in a 2:1 ratio. Subjects will be stratified by clinical site.

The list of randomized treatment assignments will be prepared by statisticians at the Emmes Corporation and included in the enrollment module of the Emmes Corporation's Internet Data Entry System (IDES). IDES will assign each volunteer a treatment code from the list after demographic and eligibility data have been entered into the system. A designated individual at each site will be provided with a treatment key, which links the treatment code to the actual treatment assignment, which will be kept in a secure place.

Instructions for use of the enrollment module are included in the IDES User's Guide. Manual back-up randomization procedures are provided in the Manual of Procedures (MOP) for use in the event that the site temporarily loses access to the Internet or the online enrollment system is unavailable.

## **5.3.2.** Masking Procedures

The applicators of vaginal gels will be selected by the unmasked Site Research Pharmacist or designated unmasked study personnel and will be distributed to masked study personnel with no labels that identify the product or applicators to the site as Monolaurin Vaginal Gel or Vehicle Placebo Gel.

The volunteers, the study personnel who perform study assessments after administration, data entry personnel at the sites, and laboratory personnel will be masked to treatment assignment. The Data and Safety Monitoring Board (DSMB) may receive data in aggregate and presented by treatment group. The DSMB may be unmasked to individual study treatment assignments, as needed, to adequately assess safety issues. Refer to the MOP for unmasking procedures.

#### 5.3.3. Reasons for Withdrawal

Any enrolled subject may withdraw or be withdrawn from the study for the following reasons:

- The subject withdraws consent
- The study is terminated
- For any reason that, in the opinion of the investigator, precludes the subject's participation in the study
- The subject no longer meets inclusion/exclusion criteria
- The subject develops an SAE that warrants withdrawal
- Other safety-related reasons at the discretion of the Principal Investigator (PI), DMID Medical Monitor, DSMB, or the subject

Any subject who has received at least one dose of study drug will be continued in efficacy and safety follow-up, if the subject agrees.

Subjects who test positive for chlamydia, gonorrhea, HIV, or are incidentally found to have a PAP result consistent with AGUS or HSIL, or have a Grade 3 laboratory abnormality will be discontinued from receiving study product if the result is available within the 3 days of study drug administration. They will be continued in follow up for safety and efficacy if they have received one dose of study drug. (PAP smears are not part of the study protocol, but may have been done outside of the study protocol by the subject's provider. Patient report of PAP smear abnormalities may be accepted as a criterion for discontinuation of study product).

If a subject develops a grade 3 laboratory abnormality while still receiving study product, they will be contacted and asked to discontinue study product and will be continued in safety and efficacy follow up. If any subject experiences a severe AE related to the study product, further doses will be discontinued. Additionally, subjects who experience a new or worsening solicited reactogenicity symptom that is grade 2 or higher will be asked to contact the study site to confirm the severity. A determination will be made whether to continue or discontinue the study product by a licensed study clinician. A subject who withdraws voluntarily from or has been discontinued from receiving further treatment will be encouraged to permit continued follow-up of AEs and to follow scheduled visits. If the subject agrees, study procedures (e.g., blood sampling for safety and vaginal sampling) may be continued.

Subjects may withdraw from participation in the study at any time. If a subject withdraws or is withdrawn prior to completion of the study, the reason for this decision must be recorded in the case report forms (CRFs). Refer to Section 7.4 for procedures to be followed if a subject withdraws from the study.

### 5.3.4. Handling of Withdrawals

In the case of subjects who fail to appear for a follow-up assessment, extensive efforts (i.e., documented phone calls and certified mail) should be made to locate or recall them, or at least to determine their health status. These efforts should be documented in the subjects' records and their health status documented in the appropriate CRF. If a subject is withdrawn prior to completion of the study, the subject will not be replaced.

# **5.3.5.** Termination of Study

The NIAID/DMID has the right to terminate this study at any time. Reasons for terminating the study may include, but are not limited to, the following:

- Incidence or severity of AEs indicating a potential health hazard
- Data recording is inaccurate or incomplete
- The Investigator has not been adhering to the protocol or applicable regulatory guidelines in conducting the study

# 6. STUDY INTERVENTION/INVESTIGATIONAL PRODUCT

# **6.1.** Study Product Description

# Monolaurin (GML)

Monolaurin, also commonly referred to as GML, is a monoglyceride surfactant. It is an ester formed from glycerol and lauric acid. Monolaurin Vaginal Gel is a clear, colorless, non-sterile glycol-based gel for vaginal administration.

FDA recognizes monoglycerides, such as monolaurin, as direct food substances that are generally recognized as safe (GRAS) (21 CFR 184.1505). Monolaurin is also considered safe as an ingredient in cosmetics and tampons (e.g., o.b.® optiBalance). As stated, monolaurin is commercially available as a food grade substance from several suppliers. HLS will use

for the initial Investigational New Drug Application (IND) phase 2 clinical trials.

This formulation promotes rapid drug distribution, as well as adequate coverage, throughout the vaginal cavity. The acidic pH keeps monolaurin in its non-ionized form in the vagina.

Monolaurin, which is practically insoluble in water, is highly soluble in this formulation.

#### Vehicle Placebo Gel

The Vehicle Placebo Gel utilizes the same vehicle formulation as used in the Monolaurin Vaginal Gel.

## 6.1.1. Acquisition

5% Monolaurin Vaginal Gel and Vehicle Placebo Gel will be provided by Hennepin Life Sciences. Upon request by DMID, the investigational product will be transferred to the following address:

DMID-Clinical Agents Repository Contract Fisher BioServices [name] [contact] [contact]

Email: [contact]

Study product will be shipped to the investigational sites upon request and approval by DMID.

## 6.1.2. Formulation, Packaging, and Labeling

The vaginal gel applicators will be packaged as a kit sufficient for twice daily administration for 3 consecutive days (six applicators). Each vaginal gel dispensing kit will be individually labeled with the protocol number, dosing instructions, recommended storage conditions, the name and address of the manufacturer, the kit number, Investigational Use Statement ("Caution: New Drug –

Limited by Federal [USA] Law to Investigational Use") and that the agent should be kept out of reach of children.

## 6.1.2.1. 5% Monolaurin Vaginal Gel

Monolaurin Vaginal Gel is a clear and colorless non-sterile glycol-based gel for vaginal administration. Monolaurin Vaginal Gel is comprised of 5% monolaurin and the following excipients:

Active test article will be comprised of 5% monolaurin prepared as pre-filled vaginal gel applicators of identical likeness to placebo. The components of the applicator are biocompatible and latex-free.

#### 6.1.2.2. Vehicle Placebo Gel

The Vehicle Placebo Gel is a clear to opaque, colorless to light gray, non-sterile glycol-based gel for vaginal administration and contains the following:

The Vehicle Placebo Gel contains the same excipients as the active product.

The Vehicle Placebo Gel will be comprised of the identical vehicle contained in the active test article prepared as pre-filled vaginal gel applicators of identical likeness to active test article. The components of the applicator are biocompatible and latex-free.

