# 6.5. Assessment of Subject Compliance with Study Intervention/Investigational Product

Study personnel will count the number of used/unused applicators contained in each returned subject kit and record this information in the test article accountability section of the subject's CRF.

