- Obtain approximately 15 cc of blood to be sent to the local Clinical Pathology Laboratory for WBC count, hemoglobin, platelet, neutrophil count, creatinine, AST, ALT, total bilirubin, random glucose, and HIV testing. If HIV testing has been performed within the past 5 days and was negative or is still pending, this test can be used for screening.
- Once all samples have been obtained, the subject will be enrolled in IDES and randomly assigned to a treatment group.
- Subjects will be counseled on proper administration and storage of the vaginal gel.
- Subjects will self-administer the first dose of the investigational vaginal gel or vehicle placebo gel with observation by study personnel while in the clinic using the first applicator in the assigned study kit.
- Subjects will receive 5 further doses (vaginal applicators with instructions) for self-administration twice-daily (morning and evening) with at least 8 hours between doses.
- Subjects will be instructed to return used applicators to the disposal bag provided in the kit to return to the clinic at Visit 2 (between Study Days 8-15).
- Review for AEs/SAEs
- Provide counseling to refrain from penile-vaginal or receptive oral sexual intercourse or insertion of any substance (other than study product), products, or objects between Visit 1 and Visit 2 and 48 hours prior to Visit 3.
- Provide memory aid and instruct subject on how to complete the memory aid for 5 days from the first day of therapy.
- Counsel subjects on avoidance of pregnancy (for all female subjects of childbearing potential).

\*If a subject's laboratory results show a positive gonorrhea, chlamydia, HIV test or grade 3 abnormality, study personnel will contact the subject to inform her of the results and instruct

her to discontinue study treatment. Telephone contact is the preferred method of contact, though initial contacts may include other forms of communication with follow-up discussions provided by telephone or in person.

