# 7.2. Visit 2 (Day 8 [Window: Days 8-15])

All subjects will return for Visit 2 on Day 8 (Window: Days 8-15) at which time the following assessments will be performed.

- Review changes in medical history:
  - Review symptoms of BV since Visit 1 and treatments for BV other than investigational drug.
  - Review all concomitant medications since Visit 1.
- Review for sexual intercourse, insertion of intravaginal substances, or objects since Visit 1.
- Review for AEs and SAEs.
- Review Memory Aid and collect applicator kit.
- Perform targeted general physical exam based on symptoms.
- Perform gynecologic exam of cervix, vagina, and vulva:
  - Assessment of vaginal discharge (quantity, color, odor, and consistency).
  - Record presence or absence of objective signs of inflammation of cervix, vagina and vulva (edema, erythema, excoriation) and presence or absence of lesions.
- Collect vaginal secretions for pH testing using pH paper 4-6.
- Perform KOH 10% wet mount on vaginal (must be performed by a licensed clinician or trained laboratory personnel) and record "whiff test": fishy (amine) odor released by the addition of a drop of 10% KOH to the vaginal discharge.
  - Evaluate for pseudohyphae or budding spores (must be performed by a licensed clinician or trained laboratory personnel).
- Perform saline wet mount (must be performed by a licensed clinician or trained laboratory personnel).
  - Evaluate and record presence and percent of 'Clue' cells in vaginal secretions.
  - Record for presence of flagellated protozoa (if positive, refer to provider for further therapy).
- Collect vaginal swabs for:
  - Gram stain of vaginal smear.
  - Swabs for culture of Gardnerella spp., Mobilluncus spp., Lactobacilli spp., Candida spp.
  - Future Use: If the subject consents to future use, one Copan ESwab in liquid amies will be collected for future use (to be transported on cold packs or ice to the research laboratory).

- Obtain approximately 10 cc of blood for:
  - WBC count, hemoglobin, platelet, neutrophil count.
  - Creatinine, ALT, AST, total bilirubin, random glucose.
- Counsel subjects to refrain from penile-vaginal or receptive oral sexual intercourse or insertion of any substance, products, or objects into vagina for 48 hours prior to Visit 3.
- Counsel subjects on avoidance of pregnancy (for all female subjects of childbearing potential).

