4.4. Treatments

4.4.1. Treatments Administered

5% Monolaurin Vaginal Gel

Monolaurin Vaginal Gel is a clear and colorless non-sterile glycol-based gel for vaginal administration. Monolaurin Vaginal Gel is comprised of 5% monolaurin and the following excipients:

Active test article is comprised of 5% monolaurin prepared as pre-filled vaginal gel applicators of identical likeness to placebo. The components of the applicator are biocompatible and latex-free.

Vehicle Placebo Gel

The Vehicle Placebo Gel is a clear to opaque, colorless to light gray, non-sterile glycol-based gel for vaginal administration and contains the following:

. The Vehicle Placebo Gel contains the same excipients as the active product.

The Vehicle Placebo Gel is comprised of the identical vehicle contained in the active test article prepared as pre-filled vaginal gel applicators of identical likeness to active test article. The components of the applicator are biocompatible and latex-free.

The first dose of Monolaurin Vaginal Gel or Vehicle Placebo Gel is administered by the subject while the subject is still in clinic. The remaining 5 doses are administered twice daily (morning and evening), with at least 8 hours between doses by the subject at home. If the subject receives her first dose after 3 p.m., she is instructed to administer the next dose the following morning.

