4.4.2. Method of Assigning Subjects to Treatment Groups (Randomization)

Enrollment of subjects is done online using the enrollment module of AdvantageEDCSM. Subjects are randomly assigned to active drug or placebo in a 2:1 ratio. The study uses a stratified, permuted blocked randomization scheme. Permuted block randomization is used to avoid the potential for serious imbalance in the number of subjects assigned to each group during the study, an imbalance that can occur in the simple randomization procedures. Stratification is by clinical site.

The randomization is prepared by statisticians at the Statistical and Data Coordinating Center (SDCC) and included in the enrollment module for the trial. AdvantageEDC assigns each subject to a treatment group after the demographic and eligibility data have been entered into the system.

The vaginal gel applicators are packaged as a kit sufficient for twice daily administration for 3 consecutive days (six applicators). Random kit numbers are provided to Fisher, the investigational product distributor, in order to ensure the associated sets of applicators are filled with the same contents (placebo or active) without unblinding the sites to what treatment is in

each kit once the shipments arrive. Each vaginal gel dispensing kit is individually labeled with the kit number. Once a subject is assigned a randomization number, a kit corresponding to the assigned treatment is distributed to the subject.

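### The placebo gel is allowed to look different from the active gel, and nothing separates the staff who see the gel from those who score cure

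*Protocol*

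**What the plan says.** **Appearance.** Protocol 6.1.2.1: "Monolaurin Vaginal Gel is a clear and colorless non-sterile glycol-based gel for vaginal administration". Protocol 6.1.2.2: "The Vehicle Placebo Gel is a clear to opaque, colorless to light gray, non-sterile glycol-based gel". SAP 4.4.1 repeats both descriptions, including "The Vehicle Placebo Gel is a clear to opaque, colorless to light gray, non-sterile glycol-based gel for vaginal administration". The active product is "prepared as pre-filled vaginal gel applicators of identical likeness to placebo", and the placebo text makes the matching statement.

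**Masking.** Protocol 5.3.2 and SAP 4.4.3 say that staff who assess women after dosing are masked. The means described is that unmasked staff hand over product carrying no identifying label.

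**Contact with the gel.** Under Protocol 7.1 the first dose is self-administered "with observation by study personnel while in the clinic using the first applicator in the assigned study kit". Under 6.3 a woman who misses a dose keeps the unused applicator. Under 6.4 the kit goes back to study personnel at Visit 2, with used items in a sealed bag for transport. Under 6.5: "Study personnel will count the number of used/unused applicators contained in each returned subject kit". Protocol 11.2 and SAP 3.3.9 name the study coordinator as the person who counts. The Visit 2 list in 7.2 includes "Review Memory Aid and collect applicator kit" and ends with the investigator's cure assessment.

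**Endpoint.** Protocol 11.3 and SAP 3.3.3 define clinical cure by four Amsel items assessed at the site. The investigator's view that more treatment is needed is enough on its own to make a failure. The Nugent score is read centrally (Protocol 8.2.2) but is not part of clinical cure.

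**The concern.** The placebo specification covers the active gel's appearance and extends beyond it. If a placebo lot falls in the opaque or gray part of that range and someone sees it, the assignment is known. The reverse does not hold, because a clear colorless gel could be either product. Any recognition therefore picks out placebo women only.

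The plan creates two occasions for seeing the gel: the observed first dose and the applicator count at Visit 2. The second falls at the visit where the primary endpoint is scored. Discharge, whiff test and clue-cell percentage leave room for judgment, and so do the investigator-opinion criterion and the relatedness of adverse events. An assessor who knows a woman is on placebo may score her less favorably, which would push the cure comparison toward active. Removing labels does nothing about a difference in the gel itself.

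**Working it through.** **Reading the text**

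| Question | What the documents give |
|---|---|
| Can the gels differ visibly? | Yes, within specification (Protocol 6.1.2.1 against 6.1.2.2; SAP 4.4.1) |
| Must they differ? | No; the placebo range includes the active gel's appearance |
| Does gel show through the applicator? | Not stated |
| Who sees the first dose? | Study personnel (7.1) |
| Who handles returned applicators? | Study personnel, counted by the study coordinator (6.4, 6.5, 11.2) |
| Are these people barred from scoring cure or relatedness? | Not stated |

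**Illustration of size**

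The plan gives no figure for scoring bias, so the bias is an assumption. Inputs from the plan are 60 vs 30 subjects and a two-sided Fisher's exact test at .05 (Protocol 11.4, 11.5).

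Formula: the rejection probability is the sum, over all (a, b) with Fisher p ≤ .05, of Bin(a; 60, p_active) × Bin(b; 30, p_placebo).

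Check against the plan: this reproduces 115 of the 121 cells of Protocol Table 4 within 2 points. The other six are three cells and their mirror images, where the table prints .38, .52 and .12 and enumeration gives .403, .562 and .141.

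The true cure rate p is set equal in both arms. Active is recorded at p and placebo at p − d, because recognition can identify placebo only.

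| True rate p | d = 0 | d = .025 | d = .05 | d = .10 |
|---|---|---|---|---|
| .20 | .036 | .040 | .059 | .159 |
| .30 | .037 | .042 | .059 | .141 |
| .40 | .040 | .043 | .057 | .121 |
| .50 | .044 | .049 | .064 | .130 |

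The d = .10 column can also be read from Table 4 (active p, placebo p − .10), which prints .15, .12, .12 and .13. The .30 row is one of the cells that differs: .12 printed, .141 enumerated.

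**What such a bias requires**

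With 30 placebo women and p = .30, about 30 × .30 = 9 cures are expected. Five points is 30 × .05 = 1.5 women; ten points is 30 × .10 = 3 women.

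If a fraction q of placebo women is recognized and a fraction s of their cures is withheld, the bias is d = p × q × s. For p = .30:

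- q = .25, s = .25: d = .019, rejection .040
- q = .50, s = .25: d = .0375, rejection .049
- q = .50, s = .50: d = .075, rejection .091

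Modest recognition with modest prejudice stays below the nominal .05. Larger combinations do not.

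**The case against.** Much of the opposing case stands.

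- The likeness statement is attached to the pre-filled applicators, not to bare gel. A reader might infer that the plan flatly claims the two gels look identical; it does not.
- The lots used may all have been clear and colorless, and the applicator may hide the gel.
- A reader might take the Visit 2 list to mean that kits are inspected before the examination. The bullets are not given as a sequence; where order matters, for sampling in 7.1, the protocol says so. Collecting a kit is also not opening it.
- The documents do not say that the observer or the coordinator also scores cure. Assessors are required to be masked, and procedures in the Manual of Procedures cannot be seen here.
- One Amsel item is pH read from paper, which leaves less room for judgment, and the central Nugent score gives a cross-check through therapeutic cure.

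Two stronger readings are tempting and are not supported. The first is a larger bias: moving recorded cure by 5 points in both arms (.25 vs .15 from a common .20) gives .155. But recognition identifies placebo only, so there is no direct route to over-scoring active.

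The second is that allocation becomes predictable, since SAP 4.4.2 says: "The study uses a stratified, permuted blocked randomization scheme". If every earlier assignment were recognized, 44%, 29% or 21% of assignments would be certain with blocks of 3, 6 or 9. If only half of placebo kits were recognizable, the shares fall to 17%, 6% and 2%. All of this requires a known block size, which neither document gives, and full recognition is not plausible when the two appearances overlap.

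What remains is that the specification allows a revealing difference and the text puts no barrier between seeing the gel and scoring the endpoint.

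**Conclusion.** The point holds as a risk to masking, worth correcting because correction is nearly free. The documents do not show that masking failed.

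The direction is clear: any recognition identifies placebo and would favor active. The size depends on assumptions the documents cannot settle: how many placebo applicators looked different, whether gel was visible, and how far knowledge changed scoring. With no true effect and a common cure rate of .20 to .40, 5 points of under-scoring in placebo alone takes the false-positive rate from .036–.040 to .057–.059. Ten points gives .121 to .159 (.141 at .30). If recognition is partial and the average bias is 2.5 points, the rate stays at .040 to .043. No conclusion about predictable allocation is drawn.

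**What to change.** 1. In Protocol 6.5 and 7.2 and SAP 4.4.3, require the returned kit to stay sealed until the Visit 2 Amsel criteria, clinical-cure judgment and adverse event assessments are recorded. The unmasked Research Pharmacist, who already holds accountability under Protocol 6.4, or an unmasked designee, then opens and counts it.
2. In Protocol 7.1, have the first dose observed by a masked staff member who does not score Amsel criteria, cure or adverse event relatedness for that woman. An unmasked observer would be a poor substitute: it puts someone who knows the assignment beside a woman whose self-report is a primary safety outcome.
3. Reconcile the gel descriptions in Protocol 6.1.2.1, 6.1.2.2 and SAP 4.4.1 with the likeness statement, and state whether gel is visible in the applicator.

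SAP 4.1 and 6.6 describe the 80-subject interim as already done, so the first two changes protect only women still to be enrolled. For the others, document how the lots actually looked and who observed and counted, and read clinical cure against the Nugent category by arm, which SAP Table 45 already tabulates.

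The cost is a few sentences, a minor scheduling constraint at small sites, and a later applicator count.
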